### **8.3. Study Restrictions**

[figure not shown]
During participation in the study, subjects must adhere to the following restrictions from Screening to the end of the Double-Blind Treatment Period unless subject safety is compromised:

- Do not use any drugs of abuse
- Do not use any investigational agents and/or devices
- Do not take any new prescribed medication, unless done so in consultation with the Medical Monitor
- Maintain current dose and regimen of all prescribed medication, unless changed in consultation with the Medical Monitor
- Do not undergo UVB treatment or plasmapheresis
- Do not change caffeine intake habits
- Do not add or change the frequency, dose, or time of administration of drugs that may cause sedation
- If routinely taking a bile acid sequestrant (eg, cholestyramine, colestipol, or colesevelam), hold the morning dose until 2 hours after study drug administration. If the bile acid sequestrant baseline dosing regimen does not allow for a 2-hour hold, hold dosing of these medications for a minimum of 1 hour after study drug administration. Alternatively, take the bile acid sequestrant at least 4 hours prior to study drug administration
- If taking antacids (eg, aluminum hydroxide, calcium carbonate, magnesium carbonate, sodium bicarbonate), withhold dosing of these medications at least 4 hours prior and 4 hours after each study drug administration

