### **7.1.3. Open-Label Extension Period**

The Open-Label Extension Period will consist of 2 study visits (Visit 7 [Week 9] and Visit 8 [Week 12]). During this period, all subjects who complete the Double-Blind Treatment Period and are still receiving study drug will receive open-label 100 mg doses of EP547. Visit 7 and Visit 8 will have a visit window of  $\pm 3$  days.

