### **8.1. Subject Inclusion Criteria**

To be eligible for study participation, all subjects must meet all the following inclusion criteria:

1. Age 18 to 80 years, inclusive
2. Has experienced self-reported daily or near-daily moderate to severe pruritus before Screening
3. Has a mean daily WI-NRS score indicative of moderate to severe pruritus (score  $\geq 4$ ) during Screening (Day -7 through Day -1); data from at least 4 of the 7 days are required to be considered an acceptable profile
4. If currently taking medications to treat the cholestatic disorder (including obeticholic acid [OCA]), must be on a stable dose for >12 weeks before Screening and plans to maintain the regimen throughout the study
5. If currently taking a fibrate, must be on a stable dose for >12 weeks before Screening and plans to maintain the regimen throughout the study
6. Either is not treated with or has been on a stable regimen with any medications to treat pruritus for >4 weeks before Screening and plans to maintain the regimen throughout the study
7. If female, must have a negative serum pregnancy test at Screening and be willing to not donate eggs from Screening until after the last dose of study drug and:
  - a. Is surgically sterile; or
  - b. Has been amenorrhoeic for  $\geq 1$  year without an alternative medical cause; or
  - c. If of childbearing potential, must agree to use at least 1 form of an acceptable method of contraception from Screening until the last dose of study drug. Acceptable birth control methods include:

---

 Women of childbearing potential are defined as those who are fertile, following menarche and until becoming postmenopausal unless permanently sterile. Permanent sterilization methods include hysterectomy, bilateral salpingectomy, and bilateral oophorectomy. A postmenopausal state is defined as no menses for 12 months without an alternative medical cause.

- Barrier methods of contraception (eg, male condom, female condom, cervical cap or diaphragm, and contraceptive sponge)
  - Combined (estrogen and progestogen containing) hormonal contraception associated with inhibition of ovulation
  - Progestogen only hormonal contraception
  - Intrauterine device
  - Intrauterine hormone releasing system
  - Bilateral tubal occlusion
  - Vasectomized partner

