### **8.4. Concomitant Medications**

Subjects are to follow the medication restrictions outlined in the inclusion and exclusion criteria ([Section 8.1](#) and [Section 8.2](#)) and subject restrictions ([Section 8.3](#)) during the study. Dosages for concomitant medications are to remain constant during the study unless needed for subject safety and instructed otherwise by the Investigator or a treating physician.

Health authority authorized or approved coronavirus disease 2019 (COVID-19) vaccines are permitted. As implied in exclusion criterion 20, investigational severe acute respiratory syndrome coronavirus 2 (SARS-CoV-2) vaccines (ie, vaccines given as part of a clinical study) are not permitted. The SARS-CoV-2 vaccine should be recorded on the Concomitant Medication electronic case report form (eCRF).

[figure not shown]
In instances where a medication is initiated prior to discussion with the Medical Monitor, the Investigator must notify the Medical Monitor as soon as he/she is aware of the use of the new medication to discuss the subject's concomitant treatment and any impact to participation in the study.

All medications taken within 14 days before Screening and details of concomitant medications from Screening through the end of study participation should be recorded as should medications taken to treat a cholestatic disorder within 12 weeks before Screening and medications known to impact pruritus taken within 4 weeks before Screening.

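### Protocol 8.3 ends sequestrant and antacid spacing with the Double-Blind Treatment Period, although EP547 dosing continues to Week 12

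*Protocol*

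**What the plan says.** Protocol 8.3 (Study Restrictions) lists its rules under one lead-in: "During participation in the study, subjects must adhere to the following restrictions from Screening to the end of the Double-Blind Treatment Period", with an exception for subject safety. The last two items concern timing around study drug. A subject who routinely takes a bile acid sequestrant is to "hold the morning dose until 2 hours after study drug administration". If the regimen does not allow that, a hold of at least 1 hour is accepted, or the sequestrant may be taken at least 4 hours before study drug. A subject taking antacids is to "withhold dosing of these medications at least 4 hours prior and 4 hours after each study drug administration".

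Protocol 8.4 (Concomitant Medications) refers back to these rules. Its first sentence begins "Subjects are to follow the medication restrictions outlined in the inclusion and exclusion criteria", goes on to name the 8.3 restrictions, and applies all of them for the duration of the study. It adds: "Dosages for concomitant medications are to remain constant during the study unless needed for subject safety".

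Protocol 7.1.3 provides that subjects who complete the double-blind period and "are still receiving study drug will receive open-label 100 mg doses of EP547". Table 4 places double-blind dosing on Days 1 to 42 and the extension on Days 43 to 85. Protocol 7.2 counts a subject as having completed the study only after all phases, including Visit 9.

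**The concern.** The spacing rules are tied to study drug administration, and the antacid rule says so for each dose. Dosing does not stop at Week 6, but the stated end date does. A site that follows 8.3 literally could tell a subject at Visit 6 that spacing is no longer needed, on the day open-label EP547 starts. A site that follows 8.4 could say the opposite.

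What is at stake is consistency of EP547 exposure in the extension. Subjects first randomized to placebo take all of their EP547 there. The planned PK summaries would not show a change in exposure during that time, because scheduled sampling ends at Week 6. The extension's WI-NRS and safety results would still be reported.

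**Working it through.** No sample size, power or alpha figure is involved. The check compares sections and counts days.

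**1. Days covered by each text.**
- 8.3, by its lead-in: Screening to the end of the double-blind period. By Table 4 the dosing days covered are Day 1 to Day 42, which is 42 days.
- EP547 dosing after that date: Day 43 to Day 85, which is 85 − 43 + 1 = 43 calendar days, or 42 if no dose is taken at the Day 85 visit (9.4.3.2 lists none).
- For a subject randomized to EP547, 42 of the 84 or 85 dosing days fall inside the 8.3 period. For a subject randomized to placebo, none of the EP547 dosing days do.

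**2. Two readings of 8.4.**
- *8.4 imports 8.3 on its own terms.* The end date comes with it. The sections then agree, and spacing lapses for the 42 or 43 open-label days.
- *8.4 sets the duration.* Since 7.2 carries the study through Visit 9, spacing covers the extension. The end date in 8.3 is then wrong for these two items.

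On either reading, the 8.3 lead-in does not fit the spacing rules.

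**3. Whether another section settles it.**
- 10.4 (Study Drug Administration): whole tablets, water, same time of day, 8-hour fast. No spacing.
- 9.4.2.5 and 9.4.3.1 (Visits 6 and 7, where open-label drug is dispensed): whole tablets with water. No spacing.
- 8.4.1 (Prohibited Concomitant Medications), as far as it can be read: no spacing rule.
- Inclusion criteria 4 to 6 in 8.1: a subject on the relevant treatment "plans to maintain the regimen throughout the study". This concerns the regimen and gives no hours of separation.

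**4. Which results the extension can touch.**
- Primary endpoint: SAP 3.4.1.1 builds the Week 6 score from the 7 days up to and including the Week 6 visit date. The score on that date is completed before the visit, so it precedes the first open-label dose. It lies inside the period 8.3 covers.
- PK: the Synopsis lists draws on Day 1 and at Weeks 1, 2, 3 and 6, the last one predose. SAP 4.4.8 summarises concentrations for the double-blind period. Visits 7 and 8 list no PK draw. Section 13 asks for an unscheduled sample after a serious adverse event, and retained samples are taken at Weeks 9 and 12, but no concentration analysis of the retained samples is stated.
- Extension efficacy: SAP 4.4.1 makes it descriptive.

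**The case against.** The strongest reply is that the two sections need not contradict each other. A cross-reference can import a section together with its limits, and the other reading leaves no gap. A reader might infer a flat conflict and a certain lapse together. The text does not support both at once: it supports one ambiguous instruction that is unsatisfactory under either reading.

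A second reply is that sequestrant users have some cover. Protocol 5.1 names bile acid-binding resins among the frontline therapies for cholestatic pruritus, so inclusion criterion 6 should usually reach them and commits them to a stable regimen. Section 8.4 holds concomitant dosages constant, and nothing readable tells anyone to change timing at Week 6. This stands in part. It favours keeping the routine of Weeks 1 to 6, but it sets no interval, and it helps less with antacids, which are not described as pruritus treatment.

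A third reply is that some text cannot be seen. Part of 8.4.1 is redacted, Table 3 is not shown, and remote-visit details are left to study manuals. That limits any statement about what sites were actually told. It does not change the 8.3 sentence, which can be read in full.

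The new-medication and stable-regimen items in 8.3 share the same end date. For those, 8.4 still requires constant dosages, and if a drug is started without prior discussion, "the Investigator must notify the Medical Monitor as soon as he/she is aware of the use of the new medication". That part is a wording mismatch only.

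**Conclusion.** The point holds, as a minor one. The end date in 8.3 does not fit two rules that are tied to study drug dosing, and 8.4 does not clearly repair it. Confidence is high on the wording and low on any practical consequence.

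A reader might measure the problem by all open-label doses, or by all placebo-first subjects who reach the extension (about 29 × 0.90 = 26.1 under the 10% withdrawal assumption in 14.4). Those counts describe the extension for everyone. The affected group is sequestrant or antacid users who would change their timing after Week 6. The documents do not give its size, and it could be zero. Nor do they state the size or direction of any effect on EP547 exposure; that spacing matters is inferred only from the existence of the rules.

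A reader might also fear for the primary result. The documents do not support that: the Week 6 comparison and the scheduled PK samples fall within the period 8.3 covers. What remains exposed is open-label EP547 exposure and the extension's descriptive summaries. Concomitant medications are recorded to the end of participation, so users could be identified afterwards.

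**What to change.** In Protocol 8.3, state that the bile acid sequestrant and antacid spacing rules apply until the last dose of study drug, including open-label dosing. This takes one sentence, or a few words in each of the two items, and changes no analysis, sample size or visit.

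Two further edits are optional drafting: repeating both rules in 10.4, where sites look for dosing instructions, and giving the other 8.3 items the same end point as 8.4.

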### **8.4. Concomitant Medications**

Subjects are to follow the medication restrictions outlined in the inclusion and exclusion criteria ([Section 8.1](#) and [Section 8.2](#)) and subject restrictions ([Section 8.3](#)) during the study. Dosages for concomitant medications are to remain constant during the study unless needed for subject safety and instructed otherwise by the Investigator or a treating physician.

Health authority authorized or approved coronavirus disease 2019 (COVID-19) vaccines are permitted. As implied in exclusion criterion 20, investigational severe acute respiratory syndrome coronavirus 2 (SARS-CoV-2) vaccines (ie, vaccines given as part of a clinical study) are not permitted. The SARS-CoV-2 vaccine should be recorded on the Concomitant Medication electronic case report form (eCRF).

[figure not shown]
In instances where a medication is initiated prior to discussion with the Medical Monitor, the Investigator must notify the Medical Monitor as soon as he/she is aware of the use of the new medication to discuss the subject's concomitant treatment and any impact to participation in the study.

All medications taken within 14 days before Screening and details of concomitant medications from Screening through the end of study participation should be recorded as should medications taken to treat a cholestatic disorder within 12 weeks before Screening and medications known to impact pruritus taken within 4 weeks before Screening.

#### **8.4.1. Prohibited Concomitant Medications**

Subjects taking immunosuppressant/immunomodulating agents may not receive live, attenuated vaccines during participation in this study. Medications with known nephrotoxic potential (eg, aminoglycosides, contrast dye, bisphosphonates, and nonsteroidal anti-inflammatory drugs) are prohibited from use during the study [REDACTED]

[REDACTED] Table 3 lists examples of excluded medications that are substrates for BCRP, OAT1, CYP2B6, or CYP2C8, or inhibitors of OAT3. If a subject receives a prohibited concomitant medication during the study, the Investigator, in consultation with the Medical Monitor, may interrupt or discontinue study drug as warranted for reasons of protecting subject safety.

## **8.5. Removal of Subjects from Therapy or Assessment**

If a subject discontinues study drug and/or is withdrawn from the study, the reason will be recorded on the eCRF page and the Sponsor will be notified promptly.

### **8.5.1. Discontinuation of Study Drug**

Study drug may be discontinued in the following instances:

- AE
- Withdrawal of consent
- Lost to follow-up
- Protocol deviation

- Investigator decision
- Sponsor decision
- Pregnancy during the study ([Section 12.2.4](#))
- Criteria met from drug-induced liver injury (DILI) monitoring to discontinue study drug ([Section 12.13.3](#))
- Other

If a subject experiences an AE that is Common Terminology Criteria for Adverse Events (CTCAE) Grade 4 or higher, the study drug must be discontinued. AE grading for severity using CTCAE criteria is described in [Section 12.1.2](#).

Subjects who terminate treatment with study drug early, regardless of the reason, will complete the early study termination evaluations as soon as possible after the last dose of study drug, ideally within 2 days after the last dose of study drug.

Whenever possible, subjects should remain in the study and complete the remaining study visits and assessments even when study drug has been discontinued. Subjects who discontinue study drug for any reason and continue with the study visits as planned through the Week 12 visit (participating only in efficacy and safety, but not PK measures) will participate in the Safety Follow-Up Visit if the last dose of study drug was administered less than 2 weeks before the Week 12 visit to ensure that at least 2 weeks of follow-up data are collected for all randomized subjects.

If a subject discontinues study drug and chooses not to complete all of the remaining study visits, the subject will have a Follow-Up Visit approximately 2 weeks ( $\pm 3$  days) after the last dose of study drug if at least 2 weeks of follow-up data have not already been collected. If a subject fails to attend the follow-up visit and has not withdrawn consent, all reasonable efforts will be made to contact the subject to ensure that he/she is in satisfactory health. All contacts and contact attempts must be documented in the subject's medical record.

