### **7.1.4. Safety Follow-Up Period**

Any subject who completes the Open-Label Extension Period or discontinues study drug (EP547 or placebo) early will complete a follow-up visit (Visit 9) approximately 2 weeks ( $\pm 3$  days) after the last dose of study drug.

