#### **11.1.1. Worst Itch Numeric Rating Scale (WI-NRS)**

Subjects will be asked to rate the severity of their worst level of itching in the past 24 hours in the morning, and at the same time of day, using the WI-NRS. The WI-NRS is an 11-point scale ranging from 0 (No Itching) to 10 (Worst Itching Imaginable) ([Phan 2012](#)) and requires approximately 1 minute to complete. Higher scores indicate greater itch severity. Itching severity scores collected via the WI-NRS have been categorized in the literature as mild (<4), moderate ( $\geq 4$  to <7), or severe ( $\geq 7$ ) ([Fishbane 2020](#), [Hirschfield 2020](#), [Levy 2020](#), [Stander 2020](#)). An example of the WI-NRS is included in [Appendix B](#).

Subjects will be instructed to complete the WI-NRS daily, in the morning, and at the same time of day, beginning at Day -14 to the Follow-Up Visit. For days that coincide with a study visit (for Visit 2 and beyond), the WI-NRS is to be completed before the visit.

The WI-NRS scores from Day -7 through Day -1 will be averaged together to confirm compliance and determine subject eligibility for continued participation regarding pruritus sensation. The average WI-NRS score using the daily values from the week before the first dose of study drug (Visit 2 [Day 1]) will serve as the baseline score. The 7 daily WI-NRS scores prior to Visit 6 (Week 6) will be averaged together for primary endpoint analyses. Data from at least 4 of the 7 days for each week are required to be considered an acceptable profile.

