### 14.2. Estimand

Consistent with the International Conference on Harmonisation (ICH) E9 (R1) addendum on estimands and sensitivity analysis in clinical trials to the guideline on statistical principles for clinical trials (FDA 2021), the definition of the attributes of the primary estimand of this study is provided in this section.

The primary estimand of the study is to assess the difference in severity of pruritus in subjects with cholestatic pruritus due to PBC or PSC treated with EP547 or placebo, as measured by change in weekly average WI-NRS after 6 weeks of randomized treatment, regardless of treatment discontinuation and use of prohibited and/or rescue medications.

The population targeted by the scientific question is defined via the inclusion and exclusion criteria as part of the protocol. A key aspect of eligibility is that subjects must have moderate-to-severe pruritus at baseline, as defined as a mean daily WI-NRS score of at least 4.

The primary endpoint to be obtained for each subject in this study to address the scientific question is the mean weekly WI-NRS score at Week 6.

Premature discontinuation from study drug and use of prohibited and/or rescue medications are the primary potential intercurrent events that could occur. The treatment policy strategy is used for the primary estimand, consistent with the intent-to-treat principle.

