**APPENDIX A. SCHEDULE OF ASSESSMENTS**

Assessment	Screening	Double-Blind Treatment					Open-Label Extension		Follow-Up	Early Study Term	Notes
		Visit 2 Day 1	Visit 3 Week 1	Visit 4 Week 2	Visit 5 Week 3	Visit 6 Week 6	Visit 7 Week 9	Visit 8 Week 12			
Study Day	Days -28 to -1	Day 1	Day 8	Day 15	Day 22	Day 43	Day 64	Day 85	2 weeks (±3 days) after last dose	≤2 days after last dose	
Visit Window	None	None b	±3 days	±3 days							
Visit Type for Hybrid Model c	Site only	Site only	Site or Remote	Site or Remote	Site or Remote	Site only	Site or Remote	Site only	Site or Remote	Site only	
General Assessments											
Informed consent	X										
Medical history	X										
Height	X										Measured with no shoes.
HIV, HAV, HBV, HCV, HEV serology	X										
IgG4	X										
Eligibility check	X	X									
Randomization via IWRS		X									Subjects will be randomized in a 1:1 ratio to 100 mg EP457 or placebo.
Dispense study drug / administer dose		X			X	X	X				Administer study drug QD as intact tablets with water. For remote visits, study drug dispensing will be conducted by a direct-to-patient courier service.
Collect study drug / assess study drug accountability and compliance					X	X	X	X		X	For remote visits, study drug collection will be conducted by a direct-to-patient courier service.
Provide questionnaire training	X										To be conducted before completing the daily WI-NRS for Day -14.

Assessment	Screening	Double-Blind Treatment					Open-Label Extension		Follow-Up	Early Study Term	Notes
Visit	Visit 1 a	Visit 2 Day 1	Visit 3 Week 1	Visit 4 Week 2	Visit 5 Week 3	Visit 6 Week 6	Visit 7 Week 9	Visit 8 Week 12	Visit 9		
Study Day	Days -28 to -1	Day 1	Day 8	Day 15	Day 22	Day 43	Day 64	Day 85	2 weeks (±3 days) after last dose	≤2 days after last dose	
Visit Window	None	None b	±3 days	±3 days							
Visit Type for Hybrid Model c	Site only	Site only	Site or Remote	Site or Remote	Site or Remote	Site only	Site or Remote	Site only	Site or Remote	Site only	
Efficacy Assessments											
WI-NRS	X	X	X	X	X	X	X	X	X	X	To be completed daily, in the morning, and at the same time of day, from Day -14 to the Safety Follow-Up Visit. For days that coincide with a study visit (for Visit 2 and beyond), it is to be completed before the visit.
5-D Itch Scale		X				X		X	X	X	
PGL-C						X		X		X	
PGL-S		X				X		X		X	
Pharmacodynamic Assessments											
Bile acids and heme metabolites		X				X					

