- Within the Open-Label Extension Period, analysis of Week 7 will be the first 7 days after the nominal Week 6 visit date or start date of open-label dosing, whichever is later; for subjects who participate in the decentralized model, there may be a gap between the nominal Week 6 visit and open-label dosing due to drug shipment considerations. Subsequent analysis visits will be counted using the next 7 days. The Week 6 WI-NRS score will be used as the Initiation of OLE score.

The Safety Follow-up Period will be anchored to the nominal Week 12 visit date. Week 13 will be the first 7 days after the nominal Week 12 visit date and Week 14 will be derived using the next 7 days.

For subjects who early terminate during the Double-Blind Treatment Period, the subject's first day of dosing (i.e., study day 1) will be the anchor date for weekly analysis visit derivations. Week 1 will be study days 2 through 8 and subsequent weekly analysis visits will be the next 7 days, deriving all applicable analysis visits until early termination.

The following additional general considerations will be applied in deriving the weekly WI-NRS scores:

- No WI-NRS daily score is to be utilized in more than one analysis visit derivation.
- For weeks where 7 calendar days are available for a given week, there must be 4 non-missing daily scores to compute the weekly score; if more than 3 daily scores are missing, the weekly score is considered missing.

• For weeks where less than 7 calendar days are available for a given week due to visit anchoring rules, at least 57% of the daily scores for the available calendar days must be reported, maintaining the same rate of reported scores as seen for a full week (i.e., 4 out of 7 days). If 6 calendar days are available for a given week, 4 non-missing daily scores are required. If 4 or 5 calendar days are available for a given week, 3 non-missing daily scores are required. If less than 4 calendar days are available for a given week, the weekly score will be considered missing.

A bi-weekly WI-NRS score will be calculated for exploratory analysis. The average WI-NRS score using the daily values from the 14 days before the first dose of study drug (including the WI-NRS score captured on the study day 1 of dosing) will serve as the baseline bi-weekly score.

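### For subjects who stop study drug and leave the visit schedule before Week 6 without withdrawing consent, the WI-NRS diary ends about 2 weeks after the last dose, usually too early for a Week 6 score

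*Protocol*

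**What the plan says.** **Diary.** Protocol Section 11.1.1 has subjects complete the WI-NRS each morning, "beginning at Day -14 to the Follow-Up Visit". Section 9.4.1.1 and Appendix A give the same end point. Nothing in either document carries the diary on to Week 6 when the Follow-Up Visit comes first.

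**After stopping drug, Section 8.5.1.** There are two routes.
- The default is to stay: "Whenever possible, subjects should remain in the study and complete the remaining study visits and assessments even when study drug has been discontinued". Efficacy measures continue, and such a subject "will participate in the Safety Follow-Up Visit if the last dose of study drug was administered less than 2 weeks before the Week 12 visit".
- The other route is for those who do not: "If a subject discontinues study drug and chooses not to complete all of the remaining study visits, the subject will have a Follow-Up Visit", about 2 weeks (±3 days) after the last dose, and only if 2 weeks of follow-up are not already in hand. Appendix A times the visit at "2 weeks (±3 days) after last dose".

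**After stopping drug, Section 7.1.4.** Here any subject who "discontinues study drug (EP547 or placebo) early will complete a follow-up visit (Visit 9) approximately 2 weeks" after the last dose, with no exception for those who stay. Figure 1 footnote b and SAP Section 3.1 say the same.

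**Estimand and analysis.** Protocol Section 14.2 defines the effect "regardless of treatment discontinuation and use of prohibited and/or rescue medications", and SAP Section 4.4.3 confirms treatment policy. The MMRM uses observed weekly scores under missing at random (Protocol Section 14.8.3). The multiple imputation in SAP Section 4.4.7.2 makes the same assumption, by treatment group.

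**Week 6 derivation.** For a subject who terminates early in the double-blind period, SAP Section 3.4.1.1 counts from the first dose: "Week 1 will be study days 2 through 8 and subsequent weekly analysis visits will be the next 7 days", continuing up to early termination.

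**The concern.** A treatment-policy estimand depends on outcome data gathered after drug is stopped. The protocol ties the end of the primary-endpoint diary to a safety visit whose date is set by the last dose, not by Week 6. A subject who stops drug in the first weeks and declines further visits, but does not withdraw consent, is therefore no longer asked for diary entries before the primary time point. Yet the diary needs no visit and takes about 1 minute a day.

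These few subjects are the ones who separate a treatment-policy effect from an on-treatment effect. Without their Week 6 scores, the MMRM and the imputation predict Week 6 mostly from weeks on drug, plus the short off-drug stretch before the diary ends. Scores that were not collected cannot be recovered later by any analysis.

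The conflict between Sections 7.1.4 and 8.5.1 adds a second risk. A site that reads 7.1.4 together with the diary instruction could take Visit 9 as the end of the diary even for a subject who is willing to stay.

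**Working it through.** **The plan's own figure.** The sample size section takes 26 completers per arm and about 10% early withdrawal: 26 / 0.9 = 28.9, rounded up to 29. This reproduces the planned 29 per arm and is not in dispute. Expected withdrawals are 0.10 × 29 = 2.9 per arm.

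**Inputs for the day count**
- Possible last-dose days in the double-blind period: Days 1 to 42 (Protocol Table 4).
- Diary end for a subject leaving the visit schedule: last dose + 14 days, range 11 to 17 (Section 8.5.1, Appendix A).
- Week 6 for an early terminator: Week 1 is Days 2 to 8, so Week 6 begins on Day 2 + 5 × 7 = Day 37 and ends on Day 43 (SAP Section 3.4.1.1).
- Minimum data: 4 scores in a full week. In a shortened week, fewer than 4 calendar days means a missing score. On either rule the diary must reach Day 40.

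**Condition.** With last dose on day L and the Follow-Up Visit g days later, Week 6 is computable only if L + g ≥ 40.

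| Follow-Up Visit | Last doses with no Week 6 score | Share of 42 days |
|---|---|---|
| Last dose + 11 | Days 1 to 28 | 28/42 = 67% |
| Last dose + 14 | Days 1 to 25 | 25/42 = 60% |
| Last dose + 17 | Days 1 to 22 | 22/42 = 52% |

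Two variants at +14 days:
- No Week 6 diary day at all falls due if L + 14 < 37, that is, for Days 1 to 22 (22/42 = 52%).
- If the diary stops the day before the visit, the count is 26/42 = 62%.

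**SAP stop rule.** If weekly scores are derived only up to an Early Termination Visit 2 days after the last dose, the condition becomes L + 2 ≥ 40. Days 1 to 37 are then lost (37/42 = 88%), even if later diary entries exist.

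**Subjects who stay.** Week 12 is Day 85. A last dose no later than Day 42 is at least 85 − 42 = 43 days before it, so Section 8.5.1 adds no Visit 9. These subjects go on to Visit 6, where Section 9.4.2.5 has staff confirm daily diary completion since Week 3. Stopping days lost by design: 0 of 42.

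**Scale.** Suppose all 2.9 planned withdrawals per arm decline visits, none withdraws consent or is lost to follow-up, and stopping days are spread evenly. The expected loss is then 2.9 × 25/42 = 1.7 Week 6 scores per arm, with a range of 2.9 × 22/42 = 1.5 to 2.9 × 28/42 = 1.9.

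**The case against.** The strongest reply is that the protocol already protects the estimand. Section 8.5.1 makes staying in the study the default and names efficacy among the measures that continue, and Section 15.8 stresses complete follow-up for all subjects. This stands, and it rules out three stronger readings.

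- **That every early stopper loses the Week 6 score.** The documents do not support this. Stayers lose none by design. The second route in Section 8.5.1 also covers a subject who attends through Week 6 and skips only Weeks 9 and 12. That subject has a Week 6 score.
- **That Section 7.1.4 will end the diary of a willing subject.** The conflict with Section 8.5.1 is real, but the loss is only possible, not shown. A site would have to put the summary rule above the specific one and overlook the diary check at Visit 6.
- **That the model fills the gap from on-drug weeks alone.** The diary runs for about 2 weeks after the last dose, and SAP Section 4.4.3 keeps data collected after discontinuation. Up to two weeks of off-drug scores can therefore contribute.

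The reply is also right about scale. The 10% is early withdrawal, which includes withdrawn consent, loss to follow-up and death (Section 8.5.2). No diary instruction recovers those. How many subjects would decline visits yet keep a diary cannot be estimated from the documents.

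What the reply leaves untouched is the group that leaves the visit schedule before Week 6 without withdrawing consent. For them the only stated diary end is the Follow-Up Visit.

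**Conclusion.** The point holds for subjects who stop study drug and leave the visit schedule before Week 6 without withdrawing consent. If the protocol is followed as written, a Week 6 score cannot be computed for 25 of 42 possible last-dose days (22 to 28 across the ±3-day window), although the primary estimand asks for it and both planned ways of handling its absence assume missing at random. This count rests on the early-terminator week definition in the SAP and on the diary stopping on the day of the Follow-Up Visit.

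The figure of 1.7 lost scores per arm is an upper bound under the assumptions stated with it. In a trial planning 26 completers per arm this is a small number, but the loss is permanent and cheap to avoid.

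Separately, Section 7.1.4, Figure 1 footnote b and SAP Section 3.1 contradict Section 8.5.1 on who has Visit 9 about 2 weeks after the last dose. The wording could be misread as ending the diary early.

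**What to change.** 1. In Protocol Sections 8.5.1, 11.1.1 and 9.4.1.1 and in Appendix A, state that every randomized subject who has not withdrawn consent continues the daily WI-NRS through at least Day 43, or the Week 6 visit if later. This should apply whatever the drug status or the timing of Visit 9, and also when further visits are declined (diary-only follow-up).
2. In SAP Section 3.4.1.1, state that weekly scores for early terminators are derived from all diary data through Week 6, so that derivation does not stop at early termination.
3. Reconcile Protocol Section 7.1.4, Figure 1 footnote b and SAP Section 3.1 with Section 8.5.1 on who has Visit 9 and when. Which visit rule applies is for the sponsor to decide. The statistical requirement is only that Visit 9 does not close the diary before Week 6.

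**Cost.** Protocol and SAP wording, a site instruction and continued diary review. The burden is about 1 minute a day in a few subjects for up to about 4 more weeks: with a last dose on Day 1 the visit falls on Day 15, and 43 − 15 = 28 days. The change does not help subjects who withdraw consent or are lost to follow-up.
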